6.1.3.1 Graphical presentation of results

A plot of the posterior probability distribution for the tBPAR rate and a bar chart corresponding to the posterior probability thresholds will be provided.

6.1.4 Supportive analyses

Kaplan-Meier estimates

In this analysis, patients who have not experienced tBPAR, will be censored with the censoring time as defined by the last contact day at or before the cut-off point (e.g., 1st IA Month 3 visit, 2nd IA Month 6 visit). The patients will be considered as completed at the date of their corresponding analysis cut-off point. In addition to the Kaplan-Meier plot, a log-rank test shall be performed to obtain estimates with CI's for each treatment arm and the difference between treatment arms.

During data review, it was noticed that some patients were switched from the randomized treatment to another regimen. Therefore in future IA's, more focus shall be placed on the Kaplan-Meier analysis.

Supportive Bayesian analysis

In addition the Bayesian analysis will be repeated with a model using a Poisson distribution to account for the patients that may switch treatment or discontinue early from the study. The following parametrization will be used:

The number of tBPAR events in group i is assumed to follow a Poisson distribution, i.e.

$$y_i = \text{Poisson}(\mu_i),$$

where μ_i is the expected number of events in group i, with

$$\mu_i = \lambda_{i,T} * t_{i,T},$$

with $t_{i,T}$ being the total follow up time in group i (times censored at treatment switch or discontinuation) up to analysis time point T and λ_i being the event rate in group i up to the analysis time point T. For sensitivity analysis of the primary analysis the analysis time point T is week 12 (i.e. week 13 visit, month 3 after transplantation). The probability of an tBPAR event occurring up to the analysis time point can then derived as $\theta_i = 1 - \exp(-\lambda_i * T)$.

The pre-defined success criteria is considered to be a difference in the probability of tBPAR between the CFZ533 arm and the control group of less than 20 percentage points with at least 60% level of proof.

$$\Pr(\theta_{CFZ533} - \theta_{SoC} < 0.20 | \text{data}) > 60\%$$

The required posterior probabilities will be estimated from simulations of the posterior distributions of $\theta_{CFZ533} - \theta_{SoC}$ and compared to the thresholds for the levels of proof.

The prior distributions will be assumed to be a non-informative Beta(1/3,1/3) for θ_{CFZ533} and an informative prior of Beta(1, 13) for θ_{SoC} .

The same outputs and presentations of the results as for the primary analysis will be provided. The analysis will be repeated for the adjudicated data when applicable.

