9.4.2 Statistical model, hypothesis, and method of analysis

Handling of missing values/censoring/discontinuations

The primary analysis only considers the events “on treatment” (apply the window defined in [Section 9.4.1](#)), thus accounting for discontinuations from the randomized treatment arm or study.

Part 1

The number of patients with tBPAR is assumed to follow a binomial distribution, i.e.,

$r_i \sim \text{Binomial}(n_i, \theta_i)$, where r_i is the number of patients with tBPAR in treatment group i, n_i is the number of patients in treatment group i and θ_i is the probability of tBPAR.

Corporate Confidential Information

The posterior mean tBPAR rate will be presented together with the 95% credible interval.

Part 2

The number of patients with tBPAR is assumed to follow a binomial distribution, i.e.,

$r_i \sim \text{Binomial}(n_i, \theta_i)$, where r_i is the number of patients with tBPAR in treatment group i, n_i is the number of patients in treatment group i and θ_i is the probability of tBPAR.

The primary efficacy analysis for the first 3 months of Part 2 evaluates whether a CFZ533 treatment arm meets the pre-defined success criteria

Corporate Confidential Information

$\Pr(\theta_{CFZ5331} - \theta_{SOC} < 0.20 \mid \text{data}) > 60\%$.

The required posterior probabilities will be estimated from simulations of the posterior distributions of $\theta_{CFZ533} - \theta_{SOC}$ and compared to the thresholds for the levels of proof.

The prior distributions will be assumed to be a non-informative Beta(1/3,1/3) for CFZ533 and an informative prior of Beta(1, 13) for placebo. This informative prior corresponds to an approximate mean response rate of 7% with a 95% confidence interval of (0.2%, 24%) and was determined via a meta-analysis of control therapies (see [Section 9.6](#)).

The posterior mean tBPAR rates for each treatment group and for the difference in mean response rates between treatments will be presented together with 95% credible intervals.

Corporate Confidential Information

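### The SAP turns to Kaplan-Meier because patients switched regimen, but its censoring rule ignores the switch, so the estimate does not deal with switching

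*SAP*

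**What the plan says.** SAP 6.1.4 places two supportive analyses of tBPAR beside the binomial Bayesian analysis of SAP 6.1.3.

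- **Kaplan-Meier.** Patients without tBPAR are "censored with the censoring time as defined by the last contact day at or before the cut-off point", with the cut-offs given as examples ("e.g., 1st IA Month 3 visit, 2nd IA Month 6 visit"). A log-rank test is planned, with estimates and confidence intervals per arm and for the difference. The text then adds: "During data review, it was noticed that some patients were switched from the randomized treatment to another regimen". Its conclusion is: "Therefore in future IA's, more focus shall be placed on the Kaplan-Meier analysis". The rule does not mention switching and does not say whether a tBPAR after a switch counts.
- **Poisson model.** This repeats the Bayesian analysis to allow for switching and early discontinuation. Follow-up is "times censored at treatment switch or discontinuation", and the success criterion is the same as in the primary analysis.

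Four other provisions bear on the point:

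- Protocol 3.1.2 and 5.5.10 keep Part 2 patients who stop study treatment in the study to Month 12, on standard of care under local practice.
- Protocol 3.1.1 describes standard of care as tacrolimus, MMF and corticosteroids.
- Protocol 9.4.2 limits the primary analysis to on-treatment events, "thus accounting for discontinuations from the randomized treatment arm or study".
- SAP section 4 analyses patients by the treatment actually received where that differs from the randomised one.

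**The concern.** The stated reason for the shift and the stated rule do not fit together. Kaplan-Meier handles switching only if the switch changes something in the estimator, either as a censoring time or as a defined event. Here it changes nothing. A patient who leaves CFZ533 on day 30 and is seen at Month 3 stays in the CFZ533 risk set throughout.

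The result is a legitimate summary of outcome whatever treatment followed, but the SAP does not label it so. A reader told that Kaplan-Meier was emphasised because of switching would take it as an on-treatment estimate. The primary objective, CFZ533 as main immunosuppressant in a CNI-free regimen, makes that reading natural. The gap also carries over: SAP 6.1.5 repeats the Kaplan-Meier analysis on adjudicated data, and SAP 6.2.3 treats graft loss, death and antibody-treated rejection in a similar way.

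**Working it through.** The documents give no switch count, switch timing or planned figure for the Kaplan-Meier analysis, so there is no stated number to reproduce. The check has three parts.

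**1. Does last contact come after the switch?** Normally yes. Protocol 3.1.2 and 5.5.10 keep such patients under observation, so the censoring time for an event-free switcher is the cut-off and not the switch day.

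**2. What does the rule do in a sample of the planned size?** Take n = 30 in the CFZ533 arm (SAP 1.4.2). Assume 6 tBPAR on days 14, 28, 42, 56, 70 and 80, event-free switchers leaving at equal spacing from day 20.5 to day 60.5, and everyone followed to day 84.

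Under the last-contact rule nobody is censored before day 84, so the product-limit estimate telescopes:

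1 − (29/30)(28/29)(27/28)(26/27)(25/26)(24/25) = 6/30 = 20.0%, for any number of switchers.

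With censoring at the switch, the risk sets shrink:

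- 3 switchers: 1 − (29/30)(27/28)(25/26)(24/25)(22/23)(21/22) = 21.4%
- 6 switchers: 1 − (29/30)(27/28)(24/25)(21/22)(19/20)(18/19) = 23.1%
- 9 switchers: 1 − (29/30)(26/27)(22/23)(18/19)(16/17)(15/16) = 25.6%

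The first rule does not respond to switching. The second does.

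**3. How large could the difference be on average?** Assumptions:

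- constant hazards;
- 3-month risk of 25% on CFZ533 (assumed) and 7% after the switch (the prior mean for control, Beta(1, 13), 1/14 = 7.1%, in SAP 6.1.3);
- a share s with a switch time uniform over Months 0 to 3, unrelated to rejection risk;
- post-switch events counted.

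Averaged over switch time, Month 3 survival for that share is (0.93 − 0.75) / ln(0.93/0.75) = 0.18/0.2151 = 0.837, a risk of 16.3%. The Kaplan-Meier reading is then (1 − s) × 25% + s × 16.3%:

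| s | Month 3 reading | Shortfall from 25% |
|---|---|---|
| 20% | 23.3% | 1.7 points |
| 30% | 22.4% | 2.6 points |
| 40% | 21.5% | 3.5 points |

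At Month 6 the on-treatment risk under the same hazards is 1 − 0.75² = 43.8%. The reading is 39.4% for s = 20% and 37.3% for s = 30%. This leans harder on the constant-hazard assumption.

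For scale, the standard error of a 25% rate in 30 patients is √(0.25 × 0.75/30) = 7.9 points.

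**The case against.** The strongest reply has four parts.

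- Kaplan-Meier is only supportive, and the Poisson analysis beside it already censors at the switch and applies the same success criterion. Together they give an all-follow-up view and an on-treatment view.
- Censoring at the switch is not clearly better. Protocol 5.5.5 moves patients to standard of care for, among other things, severe or persistent over-immunosuppression and BK nephropathy. Such patients may be at low risk of rejection, and removing them could push the curve up.
- The Month 3 shift is small beside the sampling error.
- The on-treatment window in Protocol 9.4.1 and parts of the SAP are blacked out, so a general rule may exist there.

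Most of this stands, and it limits the weight of the point. It does not remove the mismatch: the analysis singled out because of switching is the one whose visible rule disregards it, and no visible text applies an on-treatment window to it.

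A reader might infer more than the documents support:

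- **That time on tacrolimus is credited to CFZ533.** SAP 6.1.4 names neither the arm nor the new regimen. Tacrolimus is an inference from the protocol's description of standard of care.
- **That the rule must favour CFZ533.** It covers both arms, and nothing excludes tBPAR after a switch, which would count against CFZ533. The direction depends on risk being lower after the switch.
- **That it eases the proof-of-concept decision.** The criterion in SAP 6.1.3 is Bayesian and binomial. Kaplan-Meier does not enter it.
- **That it contradicts the protocol.** The on-treatment rule in Protocol 9.4.2 governs the primary analysis only.
- **That an unblinded team chose the change.** Protocol 5.4 says core team members are unblinded in Part 2, but SAP 6.1.4 does not say who carried out the data review.

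**Conclusion.** The point holds as a mismatch between purpose and rule in a supportive analysis. As written, the Kaplan-Meier estimate keeps post-switch follow-up in the arm where the patient started, reduces to the crude proportion when follow-up is complete, and makes no correction for switching. If risk after the switch is lower than on CFZ533, which is likely if the new regimen is the tacrolimus-based standard of care, the on-treatment CFZ533 rate is understated. The illustrative size is about 2 to 3 points at Month 3. It rests on assumed risks of 25% and 7%, assumed switching of 20% to 40%, constant hazards, and switching unrelated to rejection risk. The Bayesian Month 3 criterion is unaffected. The change is worth making because the SAP itself directs more attention to this analysis.

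**What to change.** In SAP 6.1.4:

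1. Keep the present Kaplan-Meier analysis, labelled as including follow-up and tBPAR after a switch. State the arm to which switchers are assigned, since the treatment-received rule in SAP section 4 does not make clear whether it covers changes during the study.
2. Add an on-treatment Kaplan-Meier analysis censored at switch or discontinuation, using the same dates and on-treatment window as the Poisson and primary analyses.
3. Report both at each cut-off, with confidence intervals for each arm and for the difference.

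The cost is one further run and a few sentences, since the Poisson model already needs the switch dates. The drawback is that censoring at the switch may be informative, which is the reason for showing both curves.

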Acute rejections should be treated with bolus methylprednisolone (other CS are acceptable at an equivalent dose) according to local practice. Recommended treatment is with at least 3 boluses of IV methylprednisolone with a minimal dose of 250 mg/bolus or at least 2 boluses of IV methylprednisolone with a minimal total dose of 750 mg.

Patients who experience steroid-resistant rejections, vascular rejections or rejections with a Banff grade \geq 2B ([Appendix 8](#)) should be discontinued from study treatment, converted to local SoC and may be treated with other anti-rejection therapies (i.e., antibody therapy).

All medications used for the treatment of suspected or confirmed acute rejections must be recorded on the Concomitant Medications eCRF under the Immunosuppressive category.

Management of signs of over-immunosuppression

CFZ533 was highly effective in preventing renal transplant rejection in NHP when used as monotherapy. Combining CFZ533 with MPA and CS after basiliximab induction may increase the risk for over-immunosuppression (e.g. BK viremia). For CFZ533 to be effective, full inhibition of CD40 signaling is required. Reducing the CFZ533 dose is not advisable, since under-dosing of CFZ533 may trigger loss of immunosuppression. In case of suspected over-immunosuppression clinical sites should first consider reducing the MPA level by 50 % or more (if MPA is completely stopped, CS may be slightly increased) with a follow up within the next weeks as per local practice. If there still are signs of over-immunosuppression, they should consider removing MPA and/ or reduce CS. If there still are signs of over-immunosuppression, or if the symptoms are severe, patient should be discontinued from CFZ533 and be switched to SoC.

Management of BK viremia

In case of diagnosed BK virus in urine, MPA levels should be reduced as a first measure as described in the Section above “Management of signs of over-immunosuppression”. Patients are considered to have significant BK viremia when their plasma PCR results report \geq 10,000 copies/mL of BK virus ([Sood et al 2012](#)).

If a patient is found to have BK viremia that reaches \geq 10,000 copies/mL in plasma, reducing/ stopping of MPA should be considered as a first measure. If patients have biopsy-proven BK nephropathy they should be discontinued from their randomized treatment and be switched to standard-of-care treatment as per local center practice.

Management of Patients with Delayed Graft Function (DGF)

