9.4 Analysis of the primary variable(s)

9.4.1 Variable(s)

Parts 1 and 2:

The primary variable is tBPAR after 3 months of treatment. For the analysis in Part 2, the total “on treatment time” in each treatment group is required.

Corporate Confidential
Information

Corporate Confidential Information

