6.1.3 Statistical model, assumptions and hypotheses

The number of patients with tBPAR is assumed to follow a binomial distribution, i.e.,

$$r_i \sim \text{Binomial}(n_i, \theta_i)$$

where r_i is the number of patients with tBPAR in treatment group i , n_i is the number of patients in treatment group i and θ_i is the probability of tBPAR.

The efficacy analysis for the first 3 months of Part 2 considers whether a CFZ533 treatment arm meets the pre-defined criteria for initiation of Part 3.

The pre-defined success criteria is considered to be a tBPAR rate difference between the CFZ533 arm and the control group of less than 20 percentage points with at least 60% level of proof.

$$\Pr(\theta_{\text{CFZ533}} - \theta_{\text{SoC}} < 0.20 \mid \text{data}) > 60\%$$

The required posterior probabilities will be estimated from simulations of the posterior distributions of $\theta_{\text{CFZ533}} - \theta_{\text{SoC}}$ and compared to the thresholds for the levels of proof.

The prior distributions will be assumed to be a non-informative Beta(1/3, 1/3) for CFZ533 and an informative prior of Beta(1, 13) for SoC. This informative prior corresponds to an approximate mean response rate of 7% with a 95% confidence interval of (0.2%, 24%) and was determined via a meta-analysis of control therapies.

The posterior mean tBPAR rates for each treatment group and for the difference in mean response rates between treatments will be tabulated together with the 95% credible intervals, the number of patients with tBPAR and the posterior probabilities of being above the thresholds, 10%, 15%, 20%, 25%.

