6.2 Secondary and exploratory objectives

6.2.1 Variables

Composite failure is a secondary variable where patients are defined to be failures if they experience any one of the following events

tBPAR

graft loss

death

Corporate Confidential Information

A date is defined for all events (e.g. borderline rejection, acute rejection) on the rejection level. In case of several events of the same type (e.g. two acute rejections) the earliest will be chosen for the analysis on the patient level.

The main part of the information for the efficacy evaluation comes from the Rejection eCRF page as well as the Biopsy eCRF page. For the derivation of the efficacy variables the

information from both pages need to be merged. The Rejection eCRF page is linked with the Biopsy eCRF page by the date of the (first) biopsy. Follow-up biopsies of the same rejection episode may be taken and are linked with the first biopsy by the date.

Borderline rejection

A biopsy is considered ‘borderline’ if, from the Biopsy eCRF page based on the pathologist’s assessment, “Borderline changes = Yes” on the Biopsy eCRF page.

Acute rejection

Acute rejections are identified in the database from the Rejection eCRF page. One of the following conditions must be met:

- Primary final clinical diagnosis indicates an acute rejection (either “acute rejection” or “acute and chronic rejection”)
- OR Antibody mediated rejection = “Yes” from the Kidney allograft biopsy eCRF page
- OR Acute T-cell mediated rejection = “Yes” from the Kidney allograft biopsy eCRF page

The date of event is the “Date rejection was first suspected” from Rejection eCRF page, or if missing the date of the first biopsy of the particular rejection episode.

Treated acute rejection

Treated acute rejections are a subset of acute rejections.

A treated acute rejection is defined if the following criteria are fulfilled:

- Acute rejection and
- “Was anti-rejection therapy administered = Yes” from the Rejection eCRF page.

The date of event is the “Date rejection was first suspected” from Rejection eCRF page, or if missing the date of the first biopsy of the particular rejection episode.

Treatments for acute rejection will be categorized into 3 groups: Steroids, Antibodies, and Other using the CRF information from the Rejection eCRF page (Were steroids administered? Was antibody treatment administered?).

Biopsy-proven acute rejection (BPAR)

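### Must SAP 6.1.4 state that a patient's time at risk in the supportive Poisson model ends at the first tBPAR?

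*SAP*

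**What the plan says.** The primary Part 2 analysis (SAP 6.1.3, protocol 9.4.2) is binomial, "where r_i is the number of patients with tBPAR in treatment group i". Success requires a posterior probability above 60% that the CFZ533 rate exceeds control by less than 20 percentage points.

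SAP 6.1.4 adds a supportive Bayesian model to allow for patients who switch treatment or stop early. In it, "The number of tBPAR events in group i is assumed to follow a Poisson distribution", with mean equal to a rate times exposure, and exposure defined as "being the total follow up time in group i (times censored at treatment switch or discontinuation) up to analysis time point T". The probability of tBPAR is then θ = 1 − exp(−λT), with T at week 12. The priors and the 20-point, 60% criterion are those of the primary analysis.

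Four other places bear on the reading:

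- SAP 6.1.4 adds that "The same outputs and presentations of the results as for the primary analysis will be provided". Those outputs include the number of patients with tBPAR.
- SAP 6.2.1 says that where a patient has several events of one type, "the earliest will be chosen for the analysis on the patient level".
- Protocol 9.4.1 says that for Part 2 the total on-treatment time "in each treatment group is required". The text after that is redacted. Protocol 9.4.2 and 9.5.3.1 both refer to windows defined in 9.4.1.
- After noting that some patients had switched regimen, SAP 6.1.4 says that in future interim analyses "more focus shall be placed on the Kaplan-Meier analysis".

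**The concern.** The transform 1 − exp(−λT) gives the probability of a first event under either of two pairings: first events over time that stops at the event, or all episodes of a Poisson process over all time. SAP 6.1.4 names neither. A programmer who follows the exposure rule word for word would count first events but leave rejecters' later on-treatment time in the denominator. Some such time is likely. Protocol 5.5.5 directs discontinuation only for some rejecters ("Patients who experience steroid-resistant rejections, vascular rejections or rejections with a Banff grade" of 2B or higher), so others may stay on regimen.

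Under a constant hazard this understates θ, and more so in the arm with more rejections, so it favours CFZ533. Two programmers could report posterior probabilities on opposite sides of 60% from the same data, and a reader might credit the gap to the adjustment for switching.

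**Working it through.** **Inputs.** n = 30 and 15 (protocol 9.6); priors Beta(1/3, 1/3) for CFZ533 and Beta(1, 13) for control; success if Pr(difference < 0.20) > 0.60 (SAP 6.1.3). Time is scaled so that T = 1. The documents give no event times, so the mean time of a first tBPAR, f, is assumed and varied from 0.1T to 0.75T.

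**1. Reproduce the plan's own figures.** Under the binomial model the first failing CFZ533 counts are 7, 8 and 9 for 0, 1 and 2 control events. These are the termination counts in protocol Appendix 3.

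**2. Literal reading, ceiling case.** The likelihood is λ^r · exp(−λE) with λ = −ln(1 − θ). First events are counted, nobody switches and every rejecter stays to week 12, so E = n. In large samples a true rate p reads as 1 − exp(−p):

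- 30%: 1 − exp(−0.30) = 25.9%
- 25%: 1 − exp(−0.25) = 22.1%
- 7%: 1 − exp(−0.07) = 6.8%

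Pr(difference < 0.20):

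| CFZ533 vs control | Binomial | Poisson, E = n |
|---|---|---|
| 7/30 vs 0/15 | 0.495 | 0.624 |
| 8/30 vs 1/15 | 0.496 | 0.641 |
| 9/30 vs 2/15 | 0.498 | 0.659 |

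Over all counts (0 to 30 and 0 to 15), 49 cells pass under this Poisson reading and fail under the binomial. Weighted by Binomial(30, p₁) × Binomial(15, p₂), they carry 15.0% of trials at true rates of 25% vs 7%, and 14.2% at 30% vs 7%.

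**3. Does a decision turn on those cells?** A binomial failure needs at least 7, 8 or 9 CFZ533 events with 0, 1 or 2 control events, and at least 10 with 3. Appendix 3 terminates at 7, 8, and then 9 for any control count above one. All 49 cells meet it.

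**4. How fast does the effect fade?** If k CFZ533 rejecters leave at mid-interval, E = 30 − 0.5k. The three cells fall back below 0.60 with k = 2 of 7 (0.590), 3 of 8 (0.591) and 4 of 9 (0.591).

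The direction can also reverse. For a true 30% the literal θ exceeds 30% once mean kept time falls below 0.30 / −ln(0.70) = 0.841T. If half the patients switch at 0.5T and all events come earlier, mean kept time is 0.5 × 1 + 0.5 × 0.5 = 0.75T, and θ reads 1 − exp(−0.30/0.75) = 33.0%.

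**5. What would ending time at the first tBPAR achieve?** With no switching, E = n − (1 − f)r in each arm. Share of trials in which the model disagrees with the binomial primary:

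| Mean event time | 25% vs 7% | 30% vs 7% | Direction |
|---|---|---|---|
| 0.1T | 15.4% | 11.7% | Poisson fails, binomial passes |
| 0.25T | 10.5% | 8.9% | Poisson fails, binomial passes |
| 0.5T | none (to one decimal) | none (to one decimal) | – |
| 0.75T | 0.7% | 1.1% | Poisson passes, binomial fails |

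For example, at 0.25T, 7/30 vs 1/15 gives 0.586 against a binomial 0.642.

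**The case for a change.** The strongest case for a change is that the formula is readable and lists its own end points without the event. The model repeats the full success criterion, is run again on adjudicated data, and protocol 9.4.1 ties the Part 2 analysis to on-treatment time, which no other readable Bayesian model here uses. Readings differ enough to cross 60%, and counting episodes moves the result again: one repeat CFZ533 episode in each of the three cells gives 0.491, 0.525 and 0.556. Two sentences would settle it.

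Part of this stands. SAP 6.1.4 does not state when time at risk ends, and the figures reproduce. The counting half is weaker. The primary definition, the requirement for the same outputs and the earliest-event rule in 6.2.1 together point to patients with a first tBPAR, so only a cross-reference is missing. A decision role for the Poisson model cannot be read from 9.4.1, because what follows there is redacted, while protocol 9.4.2 and SAP 6.1.3 both attach the criterion to the binomial model. The same redaction means one cannot say that the plan as a whole is silent on time at risk.

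**Conclusion.** No change to the plan follows. This is an unwritten definition in a supportive analysis, of a kind analysts fill in the usual way: censored times and 1 − exp(−λT) are first-event language, and the count is already indicated elsewhere in the SAP.

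The 15.0% is a ceiling. It requires that nobody switches and that every rejecter stays on regimen to week 12, whereas the SAP records that switching had already occurred and protocol 5.5.5 directs some rejecters off treatment. The effect shrinks with departures and can reverse. It leaves the binomial primary and the Kaplan-Meier estimate untouched, and every cell where the literal reading passes against a primary failure already meets an Appendix 3 count.

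Nor is the gain from rewording dependable. Ending time at the event removes the post-event exposure, but the constant-hazard assumption stays. With mean event times of 0.1T to 0.25T the clarified model departs from the primary in 10.5% to 15.4% of trials at 25% vs 7%, much like the 15.0% in the literal ceiling case. Either way the result has to be read beside the Kaplan-Meier curve, where the SAP already places its emphasis. These figures rest on full arms of 30 and 15 and on assumed event times; the text missing from protocol 9.4.1 could settle the definition outright.
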